9.1 Definitions

Adverse Event

An **adverse event** (AE) is any symptom, sign, illness or experience that develops or worsens in severity during the course of the study. Intercurrent illnesses or injuries should be regarded as adverse events. Abnormal results of diagnostic procedures are considered to be adverse events if the abnormality:

- results in study withdrawal
- is associated with a serious adverse event
- is associated with clinical signs or symptoms
- leads to additional treatment or to further diagnostic tests
- is considered by the investigator to be of clinical significance

Serious Adverse Event

Adverse events are classified as serious or non-serious. A **serious adverse event** is any AE that is:

- fatal
- life-threatening¹
- requires or prolongs hospital stay
- results in persistent or significant disability or incapacity²
- a congenital anomaly or birth defect
- an important medical event³
- positive pregnancy

¹ “Life-threatening” as defined by CTCAE Version 5.0.

² “Persistent or significant disability or incapacity” means that there is a substantial disruption of a person’s ability to carry out normal life functions.

³ Medical and scientific judgment should be exercised in deciding whether expedited reporting is appropriate in situations where none of the outcomes listed above occurred. Important medical events that may not be immediately life-threatening or result in death or hospitalization but may jeopardize the patient or may require intervention to prevent one of the other outcomes listed in the definition above should also usually be considered serious. Examples of such events include allergic bronchospasm requiring intensive treatment in an emergency room or at home, blood dyscrasias or convulsions that do not result in inpatient hospitalization, or the development of drug dependency or drug abuse. A new diagnosis of cancer during the course of a treatment should be considered as medically important.

Note: Hematologic toxicities will not be captured as serious adverse events.

All adverse events that do not meet any of the criteria for serious should be regarded as **non-serious adverse events**.

Unexpected adverse events

An adverse event related to therapy is considered unexpected (or unanticipated) if the event severity and/or frequency is not described in the investigator brochure and/or protocol.

Related adverse events

An adverse event is considered related to participation in the research if there is a reasonable possibility that an event was caused by an investigational product, intervention or research-required procedures. For the purposes of this study, "reasonable possibility" means there is evidence to suggest a causal relationship.

Preexisting Condition

A preexisting condition is one that is present at the start of the study. A preexisting condition should be recorded as an adverse event if the frequency, intensity, or the character of the condition worsens during the study period.

General Physical Examination Findings

At screening, any clinically significant abnormality should be recorded as a preexisting condition. At the end of the study, any new clinically significant findings/abnormalities that meet the definition of an adverse event must also be recorded and documented as an adverse event.

Post-study Adverse Event

All unresolved adverse events should be followed by the investigator until the events are resolved, the subject is lost to follow-up, or the adverse event is otherwise explained. At the last scheduled visit, the investigator should instruct each subject to report any subsequent event(s) that the subject, or the subject's personal physician, believes might reasonably be related to participation in this study. The investigator should notify the study sponsor ([name]) of any death or adverse event occurring at any time after a subject has discontinued or terminated study participation that may reasonably be related to this study. The sponsor ([name]) should also be notified if the investigator should become aware of the development of cancer or of a congenital anomaly in a subsequently conceived offspring of a subject that has participated in this study.

Abnormal Laboratory Values

A clinical laboratory abnormality should be documented as an adverse event if any one of the following conditions is met:

- All Grade 3 and 4 lab abnormalities not present at baseline should be captured as adverse events*.
- Any lab abnormality requiring clinical intervention or dose modification will also be captured as an adverse event*.

* This excludes lymphopenia.

Hospitalization, Prolonged Hospitalization or Surgery

Any adverse event that results in hospitalization or prolonged hospitalization should be documented and reported as a serious adverse event unless specifically instructed otherwise in this protocol. Any condition responsible for surgery should be documented as an adverse event if the condition meets the criteria for an adverse event.

Neither the condition, hospitalization, prolonged hospitalization, nor surgery are reported as an adverse event in the following circumstances:

- Hospitalization or prolonged hospitalization for diagnostic or elective surgical procedures for a preexisting condition. Surgery should **not** be reported as an outcome of an adverse event if the purpose of the surgery was elective or diagnostic and the outcome was uneventful.
- Hospitalization or prolonged hospitalization required to allow efficacy measurement for the study.
- Hospitalization or prolonged hospitalization for therapy of the target disease of the study, unless it is a worsening or increase in frequency of hospital admissions as judged by the clinical investigator.

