1.3 Clinical Data

A phase I/II study evaluating lenalidomide with rituximab for the treatment of relapsed/refractory mantle cell lymphoma was presented in 2007 at the 49th Annual Meeting of the American Society of Hematology (ASH). 18 patients were enrolled in this trial, all of which had previously been treated with rituximab. The study indicated that 70% of patients achieved responses with 30% of patients achieving complete responses when given the combination therapy.²⁷ The most common Grade 3/4 adverse events observed were neutropenia, febrile neutropenia, thrombocytopenia and myalgia. A separate study evaluated lenalidomide oral monotherapy for relapsed/refractory mantle-cell NHL in 15 patients. Objective response was noted in 53% with manageable side effects.²⁸ A study of 45 high-risk patients with relapsed or refractory CLL, treated with lenalidomide oral monotherapy, showed an overall response rate of 47%, with 9% of the patients attaining a complete remission. Fatigue, thrombocytopenia, and neutropenia were the most common adverse effects noted in 83%, 78%, and 78% of the patients, respectively.²⁹

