9.4 Reporting of Serious Adverse Events

9.4.1 Study Supporter Notification by Investigator

All serious adverse events must be reported to the study supporter, Celgene, by telephone or FAX within 24 hours of being aware of the event. A Serious Adverse Event (SAE) form on a FDA 3500A or MEDWATCH form with the Celgene Reference Number #RV-NHL-PI-296 must be completed by the investigator and faxed to the study supporter within 24 hours of being aware of the event. The initial report must be as complete as possible, including details of the causal relationship between the event and the investigational product(s) if available. Information not available at the time of the initial report (e.g., an end date for the adverse event or laboratory values received after the report) must be documented on a follow-up MEDWATCH. A final report to document resolution of the SAE is required. **A copy of the fax transmission confirmation of the SAE report to Celgene should be attached to the SAE and retained with the patient records.** Report serious adverse events by phone and facsimile to:

Celgene Corporation
 Drug Safety Surveillance
 [name]
 [name]

Toll Free:	[contact]
[contact]
[contact]
e-mail:	[contact]

At the time of the initial report, the following information should be provided:

- Study identifier
- Study Center
- Subject number
- A description of the event
- Date of onset
- Current status
- Whether study treatment was discontinued
- The reason why the event is classified as serious
- Investigator assessment of the association between the event and study treatment

Within the following 48 hours, the investigator must provide further information to Celgene on the serious adverse event in the form of a written narrative. This should include a copy of the completed Serious Adverse Event form, and any other diagnostic information that will assist the understanding of the event. Significant new information on ongoing serious adverse events should be provided promptly to Celgene.

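### The unlimited note keeping hematologic toxicities out of SAE capture conflicts with the SAE definition in the same section and can stop the 24-hour report to the supporter

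*Combined protocol and SAP*

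**What the plan says.** All the defining text is in Section 9.1 of the combined protocol and SAP.

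- The SAE list covers any AE that is fatal, is life-threatening, or "requires or prolongs hospital stay", together with disabling events, congenital anomalies, important medical events and pregnancy. None of these entries carries a hematologic exception. Footnote 1 ties life-threatening to the CTCAE definition.
- Footnote 3, on important medical events, includes among its examples "blood dyscrasias or convulsions that do not result in inpatient hospitalization".
- Directly after the footnotes comes: "Note: Hematologic toxicities will not be captured as serious adverse events".
- The next sentence supplies the residual class: "All adverse events that do not meet any of the criteria for serious should be regarded as" non-serious.
- The later paragraph on hospitalization says that an AE leading to admission "should be documented and reported as a serious adverse event unless specifically instructed otherwise in this protocol".

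The reporting rules depend on SAE status. Section 9.4.1 states: "All serious adverse events must be reported to the study supporter, Celgene, by telephone or FAX within 24 hours" of awareness. Section 9.4.3 requires an FDA report for reactions that are serious, unexpected and at least possibly drug-related, with a limit of 7 calendar days. Section 11.1 includes a regular look at the number and type of SAEs in the site's safety monitoring.

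On what to expect from the regimen, Section 1.3 says of the cited lenalidomide plus rituximab study in mantle cell lymphoma: "The most common Grade 3/4 adverse events observed were neutropenia, febrile neutropenia, thrombocytopenia and myalgia".

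**The concern.** The list and the footnote make some hematologic events serious, and the note then says that none will be captured as such. Site staff cannot follow both. The conflict falls on the class of toxicity that the protocol itself most expects: three of the four leading Grade 3/4 events in the study quoted from Section 1.3 are hematologic, and Section 1.4 gives myelosuppression as a reason for the reduced starting dose.

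What is at stake is prompt reporting. A site that follows the note literally could omit a treatment-related hematologic death from expedited reporting and still be compliant with the protocol.

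**Working it through.** No sample size, power or event figure is involved, so the check is a reading of the provisions against each other.

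**Step 1: is the note limited anywhere?** It carries no condition on grade, outcome, relatedness, expectedness or admission. No other section narrows it or restores SAE status for a severe hematologic event. Hematologic toxicity is not defined. By contrast, the laboratory-value paragraph of Section 9.1 makes one narrow, named exclusion (lymphopenia).

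**Step 2: trace three events through the text.**

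| Event | SAE list and footnote 3, Section 9.1 | Note, Section 9.1 | 24-hour report, 9.4.1 | FDA report, 9.4.3 |
|---|---|---|---|---|
| Grade 4 count, no clinical consequence | Arguably serious, if life-threatening is read from the CTCAE grade alone | Excluded | Not started | Unlikely to apply; such cytopenias are expected |
| Admission for febrile neutropenia | Serious (hospital stay) | Unclear, because the term is undefined | Not started if the note covers it | Often not due in any case, since Section 1.3 describes the event |
| Death from a hematologic toxicity | Serious (fatal) | Excluded | Not started | In doubt if unexpected and possibly related |

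The first row is the case in which an exclusion makes sense. The third row is the case in which it does not.

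**Step 3: does the residual rule settle the third row?** No. Only an AE that meets none of the seriousness criteria is non-serious. A fatal hematologic toxicity meets a criterion, so it is not non-serious, yet the note bars it from capture as an SAE. It fits neither class.

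**Step 4: does the hospitalization paragraph add to the conflict?** No. It allows exceptions made elsewhere in the protocol, and the note can be read as one. For admitted patients the conflict is therefore with the SAE list, which has no such opening. For fatal and life-threatening events no exception is provided anywhere.

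**Step 5: what still catches the event?** Grade 3 and 4 laboratory abnormalities other than lymphopenia that were not present at baseline are recorded as AEs (9.1), as are treatment-emergent AEs generally (9.2). The principal investigator reviews AEs as they occur (11.1). The medical monitor reviews all AEs at least quarterly and may recommend reporting of events not yet reported (11.2). Interim toxicity analyses are periodic (11.3). Local committees are informed under institutional rules that the protocol does not set out (9.4.2). None of these provisions sets a 24-hour clock for an on-study hematologic event.

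**The case against.** The strongest defence is that the note was meant for uncomplicated cytopenias. With life-threatening tied to CTCAE, every Grade 4 count could otherwise generate an SAE form in a population where low counts are expected. That purpose is reasonable, and an exclusion limited to it would be sound. However, the text does not contain that limit.

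A second defence is that oversight does not depend on SAE status. Much of this stands. A reader might infer that the medical monitor and the DSMC work from SAE counts and would lose sight of these events. The documents do not say so: the monitor reviews all AEs, the DSMC audits study documents and randomly selected cases, and the interim analyses concern toxicity. The SAE tally mentioned is the one in the site's own monitoring under Section 11.1. Nor is an SAE rate a study endpoint. The safety objective (2.2.3) is the toxicity profile, analysed in all treated subjects (7.12), and hematologic toxicity stays in it.

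A third defence concerns the FDA. A report needs unexpectedness and possible relatedness as well as seriousness, and the expected cytopenias would usually fail the first of these. It can also be argued that an event remains serious by definition even when it is not captured as an SAE. A reader might infer that the note blocks FDA reporting outright. The documents support only doubt, and only for unexpected, possibly related hematologic events.

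None of these defences restores the 24-hour report to the supporter for a fatal or hospitalised hematologic event that the note covers.

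**Conclusion.** The inconsistency is real and the section is wrong as written. The conflict lies within Section 9.1, between the note on one side and the SAE list and the blood-dyscrasia example on the other.

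The consequences assume that sites treat the note as governing. On that assumption, a fatal hematologic toxicity does not start the 24-hour report and drops out of the Section 11.1 SAE assessment. The same holds for an admission, if the event counts as a hematologic toxicity. The effect on FDA reporting is a doubt confined to unexpected, possibly related events. The weakness is in classification and speed of reporting; the events are still recorded and reviewed as AEs.

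The size cannot be put as a number. A reader might apply the 78% rates for neutropenia and thrombocytopenia in Section 1.3 to the 45 planned subjects. Those rates come from lenalidomide monotherapy in CLL, with no grade or seriousness given, and do not estimate how many SAEs would go unreported. The relevant quantity is the rate of fatal, life-threatening or hospitalised hematologic events, which the documents do not give.

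**What to change.** Reconcile Sections 9.1 and 9.4 as follows.

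- Limit the note to cytopenias recorded only as a laboratory grade, and say that this includes Grade 4 values that would count as life-threatening by CTCAE grade alone.
- State that a hematologic event is captured and reported as an SAE under 9.1 and 9.4 if it is fatal, clinically life-threatening, requires or prolongs hospitalisation, is disabling, or is an important medical event.
- Define hematologic toxicity for this purpose, and say whether febrile neutropenia and bleeding with a low platelet count fall within it.

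The cost is a few sentences of protocol wording and some additional SAE forms. Treatment, sample size and the planned analyses are unchanged.

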9.2 Recording of Adverse Events

At each contact with the subject, the investigator must seek information on adverse events by specific questioning and, as appropriate, by examination. Information on all adverse events should be recorded immediately in the source document, and also in the appropriate adverse event module of the case report form (CRF). All clearly related signs, symptoms, and abnormal diagnostic procedures results should be recorded in the source document, though should be grouped under one diagnosis.

All treatment-emergent adverse events occurring during the study period (after initiation of study treatment) must be recorded. The clinical course of each event should be followed until resolution, stabilization, or until it has been determined that the study treatment or participation is not the cause. Serious adverse events that are still ongoing at the end of the study period must be followed up to determine the final outcome. Any serious adverse event that occurs after the study period and is considered to be possibly related to the study treatment or study participation should be recorded and reported immediately.

Toxicity will be scored using CTCAE Version 5.0 for toxicity and adverse event reporting. A copy of the CTCAE Version 5.0 can be downloaded from the CTEP homepage (https://ctep.cancer.gov/protocolDevelopment/electronic_applications/ctc.htm). All appropriate treatment areas should have access to a copy of the CTCAE Version 5.0. All adverse clinical experiences, whether observed by the investigator or reported by the patient, must be recorded, with details about the duration and intensity of each episode, the action taken with respect to the test drug, and the patient's outcome. The investigator must evaluate each adverse experience for its relationship to the test drug and for its seriousness.

The investigator must appraise all abnormal laboratory results for their clinical significance. If any abnormal laboratory result is considered clinically significant, the investigator must provide details about the action taken with respect to the test drug and about the patient's outcome.

9.3 Reporting of Adverse Events

9.3.1 Pregnancies

Pregnancy of a female subject or the female partner of a male subject occurring while the subject is on lenalidomide or within 4 weeks after the subject's last dose of lenalidomide are considered expedited reportable events. If the subject is on lenalidomide, it is to be discontinued

immediately and the subject is to be instructed to return any unused portion of lenalidomide to the Investigator. The pregnancy must be reported to Celgene Corporation Worldwide Drug Safety Surveillance (WWDSS) within 24 hours of the Investigator's knowledge of the pregnancy by phone and facsimile using the SAE Form.

The Investigator will follow the pregnant female until completion of the pregnancy, and must notify Celgene Corporation Safety Surveillance of the outcome as specified below. The Investigator will provide this information as a follow-up to the initial SAE.

If the outcome of the pregnancy meets the criteria for immediate classification as a SAE (i.e., spontaneous abortion [any congenital anomaly detected in an aborted fetus is to be documented], stillbirth, neonatal death, or congenital anomaly), the Investigator should follow the procedures for Expedited Reporting of SAEs to Celgene (i.e., report the event to Celgene Corporation Drug Safety Surveillance by facsimile within 24 hours of the Investigator's knowledge of the event).

Any suspected fetal exposure to lenalidomide must be reported to Celgene within 24 hours of being made aware of the event. The pregnant female should be referred to an obstetrician/gynecologist experienced in reproductive toxicity for further evaluation and counseling.

All neonatal deaths that occur within 30 days of birth should be reported, without regard to causality, as SAEs. In addition, any infant death after 30 days that the Investigator suspects is related to the in utero exposure to lenalidomide should also be reported.

In the case of a live "normal" birth, Celgene Corporation Drug Safety Surveillance should be advised as soon as the information is available.

Celgene Drug Safety Contact Information:

Celgene Corporation
Drug Safety Surveillance
[name]
[name]

Toll Free: [contact]
[contact]
[contact]
e-mail: [contact]

9.3.2 Adverse Event Reporting Period

The study period during which adverse events must be reported is normally defined as the period from the initiation of any study procedures to the end of the study treatment follow-up. For this study, the study treatment follow-up is defined as 30 days following the last administration of study treatment.

9.4 Reporting of Serious Adverse Events

9.4.1 Study Supporter Notification by Investigator

All serious adverse events must be reported to the study supporter, Celgene, by telephone or FAX within 24 hours of being aware of the event. A Serious Adverse Event (SAE) form on a FDA 3500A or MEDWATCH form with the Celgene Reference Number #RV-NHL-PI-296 must be completed by the investigator and faxed to the study supporter within 24 hours of being aware of the event. The initial report must be as complete as possible, including details of the causal relationship between the event and the investigational product(s) if available. Information not available at the time of the initial report (e.g., an end date for the adverse event or laboratory values received after the report) must be documented on a follow-up MEDWATCH. A final report to document resolution of the SAE is required. **A copy of the fax transmission confirmation of the SAE report to Celgene should be attached to the SAE and retained with the patient records.** Report serious adverse events by phone and facsimile to:

Celgene Corporation
 Drug Safety Surveillance
 [name]
 [name]

Toll Free:	[contact]
[contact]
[contact]
e-mail:	[contact]

At the time of the initial report, the following information should be provided:

- Study identifier
- Study Center
- Subject number
- A description of the event
- Date of onset
- Current status
- Whether study treatment was discontinued
- The reason why the event is classified as serious
- Investigator assessment of the association between the event and study treatment

Within the following 48 hours, the investigator must provide further information to Celgene on the serious adverse event in the form of a written narrative. This should include a copy of the completed Serious Adverse Event form, and any other diagnostic information that will assist the understanding of the event. Significant new information on ongoing serious adverse events should be provided promptly to Celgene.

